**Current Version: 2.0**

### **Revision History**

Version Number	Release Date	Section	Change	Reason for Change
1.0	FEB 18 2020	N/A	N/A	Initial Release
2.0	AUG 31 2020	Multiple	
 
• Incorporate FDA feedback on Statistical Analysis Plan (sample size re-calculation, adoption of bootstrap methodology, treatment of normal tissue pathology results and recuts, additional endpoint regarding discordant unaided and aided results, etc.)
 
• Minor update to exclusion criteria regarding bowel prep based on principal investigator clinical experience
 
• Other minor content and administrative updates
 
	Incorporated feedback from FDA Pre-submission Q181327/S003

## Protocol Synopsis

Evaluation of the Clinical Performance of an Investigational Real-Time Colorectal Polyp Clinical Decision Support Device (CDSD)	
Study Objective(s)	The study objective is to establish the efficacy of the colorectal polyp CDSD in clinical use.
Planned Indication(s) for Use	
The colorectal polyp Clinical Decision Support Device is intended to support authorized healthcare professionals in increasing histological prediction accuracy of physician-identified diminutive (<math>\leq 5\text{mm}</math>) polyps during colonoscopy for documentation and comparison with pathology.
 
The device does not mark, highlight, or direct users' attention to a specific location in the original image. The device is not intended to replace histopathological sampling as a means of diagnosis.

Test Device	The investigational device consists of software residing on a dedicated computer enabling display of a polyp histology prediction (Adenoma or Non-Adenoma) in the Picture-in-Picture area of the endoscopic screen during colonoscopy procedures when Narrow Band Imaging (NBI) is engaged. The CDSD-aided endoscopist makes a final prediction of histology considering CDSD output.
Control Device	Unaided endoscopist prediction of polyp histology using NBI.
Study Design	Prospective, single arm, multicenter study
Planned Number of Subjects	A minimum of 2,400 subjects will be enrolled in order to obtain predictions on at least 1,918 diminutive polyps. It is anticipated that the study will take up to 6 months to complete.
Investigational Sites	Up to seven investigational sites in the USA will be utilized.
Co-Primary Endpoint(s)	Sensitivity and Specificity of CDSD-aided endoscopist predictions compared with unaided NBI prediction on the same polyp.
Additional Endpoints	
 
Number, proportion, unaided NBI prediction and pathology result of diminutive polyps detected by the endoscopist and confirmed by pathology for which CDSD does not return a prediction.
 

## Evaluation of the Clinical Performance of an Investigational Real-Time Colorectal Polyp Clinical Decision Support Device (CDSD)

	
 
2. Sensitivity, specificity, NPV, PPV of unaided endoscopist prediction using white light compared with pathology.
 
3. Sensitivity, specificity, NPV, PPV of unaided endoscopist prediction using NBI compared with pathology.
 
4. Sensitivity, specificity, NPV, PPV of CDSD prediction compared with pathology.
 
5. Sensitivity, specificity, NPV, PPV of CDSD-aided endoscopist prediction compared with pathology.
 
6. Number, proportions and pathology results for diminutive polyps with discordant unaided predictions using NBI and aided predictions with CDSD.
 

Method of Assigning Subjects to Treatment	
Consecutive subjects presenting for colonoscopy and meeting the pre-procedure entrance criteria will be consented and screened. Subjects meeting all the entrance criteria will be enrolled and undergo colonoscopy per the standard of care with the added use of CDSD.
 
After detection of a polyp by the endoscopist, the user will make three histological predictions (adenoma or non-adenoma):
 
 
1) using white light
 
2) using NBI
 
3) using CDSD
 

Visit Schedule	
 
1. Screening (Clinic Visit) 
 
a. Informed consent
 
b. Pre-procedural entrance criteria
 
 
 
2. Baseline (Clinic Visit) 
 
a. Demographics
 
b. Relevant medical history
 
 
 
3. Procedure (Clinic Visit) 
 
a. Colonoscopy procedure
 
b. Procedural entrance criteria
 
 
 

## Evaluation of the Clinical Performance of an Investigational Real-Time Colorectal Polyp Clinical Decision Support Device (CDSD)

	
 
c. Unaided endoscopist prediction using white light
 
d. Unaided endoscopist prediction using NBI and confidence level (high or low)
 
e. CDSD prediction
 
f. CDSD-aided endoscopist prediction and confidence level (high or low)
 
 
4. Immediate Post Procedure Evaluation (Lab results only)
 
 
a. Pathological results
 
 
5. End of Study
 
 
a. End of study will be reached after final pathology results have been obtained (typically within one to two weeks of the procedure).
 

Study Duration	Each subject's study participation will end when the final pathology results are obtained. Study enrollment is anticipated to take up to 6 months to complete.
Key Patient Inclusion Criteria	
 
1. <math>\geq 18</math> years of age
 
2. Willing and able to provide informed consent
 
3. Subjects undergoing colonoscopy
 

Key Patient Exclusion Criteria	
 
1. Polyposis syndromes including Familial Adenomatous Polyposis Syndrome
 
2. Inflammatory Bowel Disease
 
3. Hereditary Non Polyposis Colorectal Cancer
 
4. Severe coagulopathy
 
5. Subjects scoring less than 6 on the Boston Bowel Prep Score.
 
6. No diminutive polyps detected during colonoscopy
 

### Statistical Methods

Primary Statistical Hypothesis	The co-primary effectiveness endpoint is the sensitivity and specificity of CDSD-aided endoscopist prediction.
---------------------------------------	--

	$Sensitivity (Sn) = \frac{TP}{TP + FN} \quad Specificity (Sp) = \frac{TN}{TN + FP}$ 
The hypothesis for Sensitivity is:
 $H_0_{Sn}: Sn_{CDSD\text{-aided}} \leq Sn_{CDSD\text{-unaided}}$ $H_1_{Sn}: Sn_{CDSD\text{-aided}} > Sn_{CDSD\text{-unaided}}$ 
The hypothesis for Specificity is:
 $H_0_{Sp}: Sp_{CDSD\text{-aided}} \leq Sp_{CDSD\text{-unaided}}$ $H_1_{Sp}: Sp_{CDSD\text{-aided}} > Sp_{CDSD\text{-unaided}}$ 
The overall hypothesis tested is that the CDSD-aided endoscopist predictions of polyp histology will have superior sensitivity and specificity as compared with the unaided endoscopist predictions of histology on the same polyps.
 
<math>H_0: H_0_{Sn} \text{ or } H_0_{Sp}</math>
 
<math>H_1: H_1_{Sn} \text{ and } H_1_{Sp}</math>

Statistical Test Method	
Bootstrap resampling 95% confidence intervals for the difference between CDSD aided and unaided sensitivity and specificity, with bootstrap resampling performed first at the endoscopist level, then at the patient level.

Sample Size Parameters	
Based on a review of the literature, without CDSD, the operator sensitivity is presumed to be 88% and the specificity is presumed to be 58% across all operators. The operator sensitivity with CDSD is presumed to be 92% and the specificity with CDSD is presumed to be 73% across all operators based on validation testing. In order to demonstrate the primary endpoint with 80% power and one-sided significance level of 2.5% a minimum of 2400 subjects and 40 endoscopists are required. Assuming 52% of subjects will have one or more diminutive polyps, 1.81 diminutive polyps per subject having at least one diminutive polyp and an adenoma prevalence of 58% yields a minimum requirement of 1918 polyps.

## 1 Introduction

[figure not shown]
Screening colonoscopy is considered the gold standard for colorectal cancer detection and prevention in the United States. Central to screening colonoscopy is the detection of adenomatous lesions. Adenomas are considered neoplastic lesions and their removal during colonoscopy is thought to disrupt the adenoma-carcinoma progression. Their presence also influences the probability that an average-risk individual will develop colon cancer and so the number and size of adenomas detected during colonoscopy are a critical part of the process in calculating a patient's post-polypectomy colon cancer surveillance interval. One hallmark of adenomas and advanced neoplastic lesions is their enrichment with capillaries compared with normal colon mucosa and non-neoplastic polyps. Olympus' Narrow Band Imaging (NBI) is an endoscopic visualization method and adjunctive tool, cleared via 510(k) (K131780) in which broad spectrum white light illumination is filtered into bands of violet and blue light. Preferential absorption of this light by oxy-hemoglobin in red blood cells residing in capillaries and vessels of the mucosa leads to their accentuation under NBI observation.

Over the last decade researchers have validated a handful of classification systems using NBI to accurately differentiate colorectal polyps as adenomatous or non-adenomatous based on color, presence and structure of vessels and mucosal surface patterns. The NBI International Colorectal Endoscopic (NICE) Classification is one such system that was specifically created for simple characterization of diminutive ( $\leq 5\text{mm}$ ) and small ( $< 10\text{mm}$ ) polyps with non-magnifying endoscopes commonly available in Western nations and experienced endoscopists have reached high levels of diagnostic accuracy in visual assessments relative to pathological analysis. Despite this, application of NBI for real-time polyp characterization by community-level and non-expert endoscopists have yielded mixed results for performance, possibly due to variation in endoscopist skill, attention to detail or motivation.

Characterizing diminutive colorectal polyps as adenomatous and non-adenomatous, the two major classes of colorectal lesions, remains a clinical challenge for many practicing endoscopists. An adjunctive tool such as CDSD may aid in this distinction by increasing the number of accurate predictions relative to ground truth pathological analysis. The proposed study seeks to establish the effectiveness of CDSD as an adjunctive tool to assist endoscopists in the assessment of diminutive colorectal polyps.

## 2 Device Description

The investigational device consists of clinical decision support software (CDS) hosted on a dedicated, non-networked, medical accessory computer (the colorectal polyp Clinical Decision Support Device, hereinafter referred to as 'the Device' or 'CDSD'). The Device connects directly to the Olympus CV-190 Video Processor (non-investigational) and sits on the open bottom shelf of the medical cart while in use. See Figure 2-1 and Table 2-1 for details.

**Figure 2-1: System Overview****Table 2-1: CDSD Hardware Specification**

Dimensions	18.75" wide x 8.0" high x 20.5" deep
Processor	Intel i7
Memory	16GB DDR4
Hard Drive	Solid State Drive, Enterprise Grade
GPU	nVidia Quadro P4000
Capture Card	HD-SDI input/output
USB Ports	2x Front/ 4x Rear
Operating System	Windows 10 IOT, 64 bit

The Device connects to the Olympus CV-190 Video Processor through two HD-SDI cables, enabling the receipt of the endoscopic signal from the CV-190, and sending of the Device's output to the CV-190 for display in the Picture-in-Picture (PiP) region of the endoscopic monitor.

[figure not shown]
The software composing the Device contains two modules:

- User Interface module (the “UI module”), and
- Artificial Intelligence module (the “AI module”).

### 2.1.1 User Interface Module

The CDS continuously receives the raw (unfiltered) endoscopic video stream from the CV-190 video processor, and integrates the data from the AI module into the final information displayed by the UI module. This information is presented as both a text output and progress bar in the PiP region of the monitor alongside the raw video output. The presented text output is either ‘non-adenoma’, ‘adenoma’ or no text is displayed where model prediction repeatability is not achieved, too variable over consecutive frames or no polyp is present in the video stream that is identifiable to the AI module. The progress bar illustrates model prediction repeatability and is color-coded to identify suspected adenoma/non-adenoma. Figure 2-2 depicts these different outputs.

**Figure 2-2: Graphical User Interface of CDS**

Empty Bar
 
 
• NBI is not engaged, OR
 
• NBI is engaged but the software cannot classify the polyp or no polyp is present
 
	 
ELAI.Colon.ID:19.00.01.01
 
CAUTION: Investigational device. Limited by Federal law to investigational use.

Filling Bar
 
 
• The software is classifying a polyp
 
	 
ELAI.Colon.ID:19.00.01.01
 
CAUTION: Investigational device. Limited by Federal law to investigational use.

Result: Non-Adenoma
 
 
• The software has repeatedly classified the suspected polyp and has returned a result of Non-Adenoma.
 
	 
ELAI.Colon.ID:19.00.01.01
 
CAUTION: Investigational device. Limited by Federal law to investigational use.

Result: Adenoma
 
 
The software has repeatedly classified the suspected polyp and has returned a result of Adenoma.
 
	
---	--

The information of the investigational device does not obfuscate the primary endoscopic video on the monitor, nor does it mark, highlight, or direct users' attention to a specific location on the endoscopic video. The investigational device's output is clearly identified as 'Investigational Device' (refer to Figure 2-2) to ensure the endoscopist does not mistake it for the primary endoscopic video.

### 2.1.2 Artificial Intelligence Module

The AI module is composed of a static AI model, trained on raw endoscopic videos (video recordings) originating from unaltered recordings of colorectal polyps, specifically of diminutive polyps ( $\leq 5$  mm) with proven pathology. The AI module takes raw endoscopic data as input (full frame, no segmentation), and outputs two data streams:

- (1) Classification of video frames into white light mode versus Olympus CV-190 NBI mode, and
- (2) Classification of endoscopic images of the NBI class (only) into 'adenoma' and 'non-adenoma'.

Information from the AI module is presented to the operator, via the User Interface module described in section 2.1.1 only when the Olympus CV-190 processor is engaged in the NBI mode by the operator.

The investigational Device connects to and is used with the Olympus EVIS EXERA III, which includes the CV-190 Video Processor (CV-190). The EVIS EXERA III system was last cleared via 510(k) K131780. During the clinical study, the EVIS EXERA III system will be used within its cleared indication for use.

Further, table 2-2 provides a complete listing of non-investigational devices needed or recommended for use in the clinical study.

**Table 2-2:** Non-Investigation Devices Required/Recommended

Device *	Manufacturer	Description	Required or Recommended
CV-190	Olympus	Endoscopic video processor	Required
CLV-190	Olympus	Endoscopic light source	Required
OEV-262	Olympus	Endoscopic video monitor	Recommended
One or more of the following colonoscopes:			
CF-HQ190L	Olympus	Colonoscope	Required
PCF-H190(D)L	Olympus	Colonoscope	Required

### 3 Study Objectives

The study objective is to establish the efficacy of the colorectal polyp CDSD in clinical use.

### 4 Study Endpoints

Co-Primary Endpoint:

Sensitivity and Specificity of CDSD-aided endoscopist predictions compared with unaided prediction on the same polyp.

Secondary Endpoints:

[figure not shown]
1. Number, proportion unaided NBI prediction and pathology result of diminutive polyps detected by the endoscopist and confirmed by pathology for which CDSD does not return a prediction.
2. Sensitivity, specificity, NPV, PPV of unaided endoscopist prediction using white light.
3. Sensitivity, specificity, NPV, PPV of unaided endoscopist prediction using NBI.
4. Sensitivity, specificity, NPV, PPV of CDSD prediction.
5. Sensitivity, specificity, NPV, PPV of CDSD-aided endoscopist prediction.
6. Number, proportions and pathology results for diminutive polyps with discordant unaided predictions using NBI and aided predictions with CDSD.

### 5 Study Design

The study shall be a prospective, single arm, multicenter study. Endoscopists comprising a range of clinical experience will be invited to participate in the study at each site. All

participating endoscopists will receive an overview of the NICE classification to guide their unaided and CDSD-aided assessments as well as instruction on the use of CDSD.

For each participating endoscopist, consecutive subjects presenting for colonoscopy and meeting the pre-procedure entrance criteria will be consented and screened. Consented subjects meeting all the entrance criteria will be enrolled and undergo colonoscopy per the standard of care with the added use of CDSD. CDSD-unaided and CDSD-aided predictions will be compared with the ground truth of histopathology. Presuming at least 40 endoscopists participate, each endoscopist will make approximately 60 predictions on diminutive polyps through the course of the study.

**Figure 5-1: Procedure Flow**

During the procedure, the endoscopist will insert the colonoscope to the cecum as per standard of care. Examination will be under white light illumination. Typically during withdrawal, but also during insertion at the discretion of the endoscopist, identified lesions

will have their location, size and shape documented. The endoscopist will inspect the lesions and estimate the size of lesion (diameter in mm) using a device such as the tip of a biopsy forceps or snare catheter tip as is common practice. Diminutive size is defined as a diameter  $\leq 5$ mm. For diminutive polyps, an initial histology prediction will be made in white light as ‘Adenoma’ or ‘Non-adenoma’ based on the endoscopist’s experience and training. NBI will be engaged and the endoscope tip will be steadied with the lesion centered. The endoscopist will be blinded to the CDSD result. The endoscopist will make a second prediction of polyp histology as ‘Adenoma’ or ‘Non-adenoma’ using NICE classification criteria (see Figure 5-1). NICE Type 1 will be defined as Non-Adenoma and NICE Type 2 will be defined as Adenoma. The endoscopist must make a prediction and is not permitted to render an ‘unsure’ or ‘don’t know’ prediction. The endoscopist will state their level of confidence in the prediction.. See Table 5-1 for a description of the NICE classification and criteria used to predict diminutive polyp histology.

**Table 5-1: NBI International Colorectal Endoscopic (NICE) Classification**

NICE Classification	Type 1	Type 2
Color	Same or lighter than background	Browner relative to background (verify color arises from vessels)
Vessels	None, or isolated lacy vessels may be present coursing across the lesion	Brown vessels surrounding white structures
Surface Pattern	Dark or white spots of uniform size, or homogeneous absence of pattern	Oval, tubular or branched white structures surrounded by brown vessels
Predicted Histology (Human or CDSD)	Non-Adenoma	Adenoma

After making their prediction using NBI alone, the endoscopist or coordinator will enable PiP to allow the endoscopist to observe the CDSD result. The CDSD result shall be recorded as 1) Adenoma, 2) Non-adenoma, or 3) No prediction after system stabilization. The endoscopist considers their initial prediction and the output of the device to make a final combined prediction of polyp histology as ‘Adenoma’ or ‘Non-adenoma’. The endoscopist will make a determination of their confidence in their prediction as either ‘high’ or ‘low’. If CDSD does not return a prediction this does not indicate that no polyp is present. More likely, this output is due to the module not being able to make a clear adenoma/non-adenoma assessment based on the training the model has received. Based on software validation testing, this is expected to occur in approximately 11-16% of the polyps. In cases that this occurs, the result will be recorded as “no prediction”. In this scenario, the endoscopist will make a final prediction without the aid of CDSD.

Polyps will be biopsied or resected as per the standard of care and placed in a separate specimen jar or polyp trap chamber and uniquely labeled as per standard procedure. The exam will continue and the steps above are repeated for each identified diminutive lesion. At the end of the procedure, polyp specimens are sent to pathology for review. The pathologist is blinded to the endoscopist predictions and CDSD prediction.

The diagnosis will be rendered by the pathologist, who is blinded to the endoscopists' polyp characterization, and the pathology report will be reviewed by the endoscopist. A CDSD-aided or CDSD-unaided prediction of Adenoma will be rendered as a True Positive when the pathological diagnosis is 'conventional adenoma' (a.k.a. tubular adenoma), tubulovillous adenoma, villous adenoma, traditional serrated adenoma (TSA), adenoma with high grade dysplasia or cancer. A CDSD-aided or unaided prediction of non-adenoma will be rendered as a True Negative when the pathological diagnosis is hyperplastic polyp, sessile serrated polyp (SSP), inflammatory polyp, lymphoid aggregate/follicle, granulation tissue or normal colonic mucosa. Diminutive polyps that are lost following resection or destroyed during pathology prior to diagnosis will be excluded from the analysis due to lack of ground truth pathology results.

In cases where the CDSD-aided endoscopist prediction and the pathology result differs, a recut and reanalysis of the tissue block will be conducted. In such cases, the second successful pathology reading will be recorded and used as the histopathological ground truth.

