### 5.3 *Justification for the Study Design*

This study design was chosen to follow current standard of care endoscopy procedures with the exception of introduction of CDSD as part of the physician's decision algorithm. Pathology remains the gold standard methodology for diagnosis in this study. The study aims to demonstrate that CDSD is capable of increasing the sensitivity and specificity of endoscopist predictions for diminutive polyp histology. The single arm design was chosen to evaluate the incremental improvement in predictive accuracy relative to the standard of care while controlling for variability in polyp presentation by using a matched pair design. Inclusion of endoscopists comprising a range of experience is intended to reflect real-life clinical practice and potential increased benefit to non-expert users. Blinding allows for independence of assessments, and comparison of results without bias.

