#### 9.1.1.2 Sample Size

In order to demonstrate the primary endpoint with 80% power and one-sided significance level of 2.5% a minimum of 40 endoscopists and approximately 2400 subjects are required. Assuming 85% of subjects have adequate bowel preparation, 52% of subjects with adequate bowel preparation have one or more diminutive polyps, 1.81 diminutive polyps per subject having at least one diminutive polyp and a 58% adenoma prevalence yields a minimum requirement of 1918 polyps.

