#### 9.1.1.3 Statistical Methods

The 95% confidence intervals for the differences between CDSD-aided and CDSD-unaided sensitivity and specificity are estimated using bootstrap resampling with resampling performed first at the endoscopist level and then at the patient level. The null hypothesis is rejected if both lower bounds of the confidence intervals are greater than 0.

$$Sn_{CDSD\text{-aided}} - Sn_{CDSD\text{-unaided}} > 0$$

$$Sp_{CDSD\text{-aided}} - Sp_{CDSD\text{-unaided}} > 0$$

The assumptions of the statistical model used to establish the sample size are:

1. There are at a minimum 40 endoscopists participating in the study and each endoscopist makes approximately 60 predictions,
2. For each endoscope (CF-HQ190 and PCF-H190) and for each class of diminutive polyp (adenoma and non-adenoma) there is an intra-cluster correlation coefficient of 0.05 for predictions made by the same endoscopist,
3. There is no correlation between an operator's sensitivity and specificity,
4. There is no correlation between predictions made by the same operator across endoscope models (CF-HQ190 and PCF-H190),
5. The distribution of adenomas and non-adenomas within subjects with more than one diminutive polyp was modelled and is described in the statistical analysis plan,
6. The values from the range of possible values for the discordant pairs (b, c, n and p) that are used to calculate sample size are reported in Tables 9-3, 9-4, 9-5 and 9-6),
7. Without CDSD, the operator sensitivity is presumed to be 88% and the specificity is presumed to be 58% across all operators for all colonoscopes. The operator sensitivity with CDSD is presumed to be 92% and specificity with CDSD is presumed to be 75% across all operators when using the CF-HQ190 colonoscope (benchtop testing data). The operator sensitivity with CDSD is presumed to be 91% and the specificity with CDSD is presumed to be 72% across all operators when using the PCF-H190 colonoscope (benchtop testing data). Combined, the operator

sensitivity with CDSD is presumed to be 92% and the specificity with CDSD is presumed to be 73% across all operators,

8. The prediction rate for CDSD with CF-HQ190 is 89% and the prediction rate for CDSD with the PCF-H190 is 84% (benchtop testing data),
9. The proportion of subjects examined with the PCF-H190 will be 50%,

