### 9.1.2 Secondary Endpoints

1. Number, proportion, unaided NBI prediction and pathology result of diminutive polyps detected by the endoscopist and confirmed by pathology for which CDSD does not return a prediction.
2. Sensitivity, specificity, NPV, PPV of unaided endoscopist prediction using white light compared with pathology.
3. Sensitivity, specificity, NPV, PPV of unaided endoscopist prediction using NBI compared with pathology.
4. Sensitivity, specificity, NPV, PPV of CDS prediction compared with pathology.
5. Sensitivity, specificity NPV, PPV of CDS-aided endoscopist prediction compared with pathology.
6. Number, proportions and pathology results for diminutive polyps with discordant unaided predictions using NBI and aided predictions with CDS.

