## 9.2 General Statistical Methods

### 9.2.1 Analysis Sets

Intention to Treat (ITT) analysis will be performed on all subjects meeting the entrance criteria. The primary endpoint will be assessed by ITT analysis on polyp level data.

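### When the device returns no prediction, does the plan leave open how the endoscopist's final call enters the primary analysis?

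*Combined protocol and SAP*

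**What the plan says.** Section 5 (text below Table 5-1) allows three recorded device results: adenoma, non-adenoma and no prediction. For the third it says: "In this scenario, the endoscopist will make a final prediction without the aid of CDSD". Section 8.4 lists the items collected: a white-light call, an NBI call with confidence, the device result, and one aided call with confidence. There is no separate item for a final call made without a device result.

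On who is analysed, Section 9.2.1 says: "The primary endpoint will be assessed by ITT analysis on polyp level data". The only polyp-level exclusion is in Section 5: "Diminutive polyps that are lost following resection or destroyed during pathology prior to diagnosis will be excluded from the analysis". Tables 9-1 and 9-2 cross the aided with the unaided call and have no third category. Section 9.1.1.3, assumption 8, puts device prediction rates of 89% (CF-HQ190) and 84% (PCF-H190) among the inputs to the sample-size model.

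On separate reporting, secondary endpoint 1 in Section 9.1.2 gives a count and a share, together with the "unaided NBI prediction and pathology result of diminutive polyps detected by the endoscopist and confirmed by pathology for which CDSD does not return" any result. Secondary endpoint 6 is "Number, proportions and pathology results for diminutive polyps with discordant unaided predictions using NBI and aided predictions with CDS"; it does not distinguish polyps with and without a device result.

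**The concern.** A call made without the device appears to be counted as a device-aided call, and nothing says so outright. The paired tables offer three possible treatments: use the recorded final call, set it equal to the NBI call, or leave the polyp out. Each gives a different estimate, and such a choice should be fixed before the data are seen.

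The final call is also a second look. If endoscopists correct their NBI call on re-inspection with no device result in view, those corrections would be credited to the device; calls spoiled on re-inspection would be charged to it. Endpoint 1 omits the final call and endpoint 6 pools all discordance, so no listed table isolates this. Section 5.3 adds "Blinding allows for independence of assessments, and comparison of results without bias", although Section 5 has the endoscopist weigh the earlier call when making the final one. At stake is the sensitivity comparison, which has the smaller expected gain and limits the power of the co-primary test.

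**Working it through.** **1. Does the planned count include no-result polyps?** Inputs are from Section 9.1.1.2: 2,400 subjects, 85% adequate preparation, 52% with a diminutive polyp, 1.81 polyps each.

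- 2,400 × 0.85 × 0.52 × 1.81 = 1,920, against the stated 1,918.
- Also multiplying by the mean prediction rate, (0.89 + 0.84)/2 = 0.865, gives 1,661.

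The stated count reproduces only without the prediction-rate factor when the stated 85% is used. This fits no-result polyps being part of the 1,918.

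**2. Size of the group.** The no-result share is 1 − 0.865 = 0.135.

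- 1,918 × 0.135 = 259 polyps (211 at 11%, 307 at 16%).
- At 58% adenoma prevalence: about 150 adenomas and 109 non-adenomas.

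**3. Effect on the expected difference.** Gain minus loss from Tables 9-3 to 9-6, with the scopes split 50/50 (assumption 9):

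- Sensitivity: 0.0859 − 0.0365 = 0.0494 and 0.0749 − 0.0475 = 0.0274; mean 0.0384.
- Specificity: 0.299 − 0.124 = 0.175 and 0.2815 − 0.1415 = 0.140; mean 0.1575.

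Suppose the tables describe only polyps with a device result (not stated). Let g be the net share of no-result polyps corrected on the second look. Then:

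- Sensitivity gain = 0.5 × (0.89 × 0.0494 + 0.84 × 0.0274) + 0.135g = 0.0335 + 0.135g.
- Specificity gain = 0.5 × (0.89 × 0.175 + 0.84 × 0.140) + 0.135g = 0.1367 + 0.135g.

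With g = 0 the loss is about 0.5 point on sensitivity and 2.1 points on specificity. Each point of g moves either estimate by 0.135 point. The documents give no value for g. Over an assumed −5 to +5 points, the sensitivity gain runs from 2.67 to 4.02 points and the specificity gain from 12.99 to 14.34.

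**4. When would inclusion flatter the device?** The gain among polyps with a result is 0.0335/0.865 = 0.0387 for sensitivity and 0.1367/0.865 = 0.158 for specificity. The pooled gain exceeds these only if g is above 3.9 points and 15.8 points respectively, that is, only if re-looking alone helps as much as the device is assumed to help.

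**5. Power.** Normal approximation for the paired difference: variance (gain + loss) − (gain − loss)² per polyp; design effect 1 + (m − 1) × 0.05 per endoscopist and scope; 40 endoscopists; one-sided 2.5%. For adenomas, m = 1,918 × 0.58/(2 × 40) = 13.9 and the design effect is 1.645.

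| Handling of no-result polyps | Sensitivity gain | SE | Power |
|---|---|---|---|
| All 1,918 at table values | 3.84 | 1.34 | 81.9% |
| Excluded (about 1,659 left) | 3.84 | 1.40 | 78.6% |
| Kept, final call equal to NBI call, tables read as result-only | 3.35 | 1.24 | 76.8% |

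The first row is close to the stated 80%. Specificity power is about 100% in each row, so sensitivity sets the joint power. The level depends on the model. A simulation with the two-stage bootstrap, using an assumed distribution of polyps per subject, gave 68%, 63% and 62% in the same order. The protocol refers its own within-subject model to SAP text not shown here, so these levels are no evidence against the stated power.

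**The case for a change.** The strongest case for a change is that three readings give three estimates and that one sentence would remove the doubt. Under the result-only reading, power also depends on g. If every second-look change goes one way, sensitivity power is about 55% at g = −5 points, 77% at zero and 88% at +5. If 12.24% of no-result calls change (the discordance in Tables 9-3 and 9-4), it is about 51%, 71% and 85%. The reading matters during conduct too, because Sections 5 and 9.2.3 trigger a recut when the aided call differs from pathology.

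Some of this stands. The inclusion rule is implied, not written. Endpoint 1 omits the final call, endpoint 6 is not split by device result, and no planned analysis shows the primary result with these calls neutralised.

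The rest carries less weight. The readings are not equally open: excluding the polyps would contradict the ITT rule and the single exclusion, and substituting the NBI call would discard a recorded value with no instruction to do so. The single final-call item answers the recut question in the same way. The power spread comes from an assumed range for g and an unstated reading of the tables. Because prediction rates are already model inputs, the dilution may be inside the stated 80%.

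These polyps are also a weak check on second-look change. With an assumed 5% to 12.24% of calls changing among 150 adenomas, the SE is √(0.05/150) = 1.8 to √(0.1224/150) = 2.9 points before clustering, against an expected gain of about 3.4. Polyps the device cannot classify may also be harder than the rest. Section 5.3 is loosely worded, but Section 5 openly has the final call build on the first, so no analyst would be misled.

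**Conclusion.** The concern identifies a missing sentence, not a wrong rule. An analyst following the text would enter each no-result polyp that has pathology, with its recorded final call as the aided call. That is also a sensible estimand: performance of the endoscopist with the device in its workflow, including the occasions when it gives no result.

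The expected consequence is conservative: up to about 0.5 point on sensitivity and 2.1 points on specificity, assuming Tables 9-3 to 9-6 cover only polyps with a result, a 13.5% no-result share and no net second-look change. If the tables cover all polyps, there is no further dilution to allow for. Inflation would need a net unaided correction above 3.9 points for sensitivity or 15.8 for specificity, and nothing in the documents suggests either.

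These polyps are already reported apart in endpoint 1. The device result, both NBI-based calls and pathology are all collected (Sections 8.4 and 8.5), so a split of endpoint 6 or a supportive run with the aided call set to the NBI call can be produced at any time. Such reporting would be useful, but it corrects no error and the primary conclusion does not depend on it. No change is called for.
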